9.3 IND Annual Reports

For trials with an IND held locally by the IU principal investigator or university, the IND Annual Report will be prepared and submitted to the Compliance Team. This report will be reviewed and approved by the DSMC prior to FDA submission.

9.4 Study Auditing and Monitoring

All trials conducted at the IUSCC are subject to auditing and/or monitoring per the Institutional DSMP. Reports will be reviewed by the full DSMC at the time of study review.

9.5 Data Management/ Oncore Reporting Requirements

The DSMC reviews data and study progress directly from Oncore; therefore, timely data entry and status updates are vital. Study data must be entered within Oncore promptly, no later than one week from study visit occurrence. Subject status in Oncore will be updated in real time, as this may affect overall trial enrollment status. Global SAEs and deviations will be reviewed on a monthly basis by the DSMC Chair directly from Oncore.

9.6 Study Accrual Oversight

Accrual data will be entered into the IU Simon Comprehensive Cancer Center OnCore system. The Protocol Progress Committee (PPC) reviews study accrual twice per year, while the PPC coordinator reviews accrual quarterly.

9.7 Oncore Safety Reporting

In addition to protocol- and regulatory-required safety reporting, all serious adverse events (SAEs) will be captured in the Oncore system within 1 business day of notification. Initial SAE reporting will include as much detail as available, with follow-up to provide complete information. Attributions will be assessed to study drugs, procedures, study disease, and other alternate etiology.

9.8 Protocol Deviation Reporting

Protocol deviations will be entered into OnCore within 5 days of discovery and reviewed by the DSMC Chair on a monthly basis. Findings will be reported to the full DSMC at the time of study review. For serious or repetitive protocol deviations, additional action may be required by the DSMC.

9.9 Data Acquisition

Case Report Forms and Data Submission: This study will utilize electronic Case Report Form completion in the OnCore® database. A calendar of events and required forms are available in OnCore® at <https://cancer.iu.edu/oncore>. The OnCore® database is a comprehensive database used by the IUSCC CTO and supported by the Indiana University Cancer Center.

Access to data through OnCore® is restricted by user accounts and assigned roles. Once logged into the OnCore® system with a user ID and password, OnCore® defines roles for each user which limits access to appropriate data.

All source documents are to remain in the patient's clinic file. All documents should be kept according to applicable federal guidelines. Clinical trial data in OnCore® are periodically monitored by the IU Simon Comprehensive Cancer Center per the DSMC Charter.

10.0 MULTICENTER GUIDELINES

10.1 Study Documents

Each participating site must submit regulatory documents (informed consents, 1572s, Financial Disclosures, IRB approval documents, Continuing Reviews, Amendments, patient brochures or recruitment material etc.) to the Coordinating Center. The Coordinating Center will provide each site with a comprehensive list of the required documents prior to study start-up, throughout the duration of the study and upon study close-out. It is the responsibility of the participating site to maintain copies of all documentation sent to the Coordinating Center.

10.2 Study Initiation

Before activating the clinical trial at each participating site, the IUSCC CTO Multicenter Network Administrator , or designee, will ensure that:

- **Full Institutional Review Board (IRB) approval** has been obtained.
- Research staff at the participating site has been trained in data entry into *OnCore*®
- A **start-up meeting** with each institution has taken place via telephone conference. The start-up meeting will cover protocol details (including eligibility

criteria, treatment plan, etc.), responsibilities of the participating investigators, and reporting procedures.

- A financial **conflict of interest statement** from each investigator has been obtained.

10.3 Patient Enrollment

After eligibility is confirmed by the participating site staff, a completed eligibility checklist, supporting source documentation, and signed consent will be sent to IUSCC for verification. The Multicenter Network Administrator, or designee, will confirm eligibility and return the enrollment information to the site. The site staff will then register the patient in OnCore®. Additional details of this process can be found in the Study Procedure Manual.

10.4 Data Monitoring

All multicenter investigator initiated trials conducted at the IUSCC are subject to data monitoring by the Multicenter Network Administrator, or designee. External sites will be notified of upcoming monitoring visits and will be expected to provide the Multicenter Network Administrator, or designee, with source documents for remote monitoring of patients. Queries will be issued in OnCore® and a detailed monitoring report will be provided to the participating site. The IUSCC will also forward any monitoring and/or auditing reports to the DSMC.

When a patient enrolled on this trial, or the trial itself, is selected for local monitoring or auditing, the participating site will forward the results to the Multicenter Network Administrator, or designee. In addition, if a participating site patient is selected for local auditing by the IUSCC DSMC, the site will be responsible for sending IUSCC de-identified source documents.

10.5 Record Retention

All documentation of adverse events, records of study drug receipt, dispensation, destruction, and all IRB correspondence will be stored in accordance with all applicable federal guidelines.

Following closure of the study, each participating site will maintain a copy of all site study records in a safe and secure location. The Coordinating Center will inform the investigator at each site at such time that the records may be destroyed.

11.0 LABELING, PACKAGING, STORAGE AND RETURN OF CLINICAL SUPPLIES

11.1 Investigational Product

The investigator shall take responsibility for and shall take all steps to maintain appropriate records and ensure appropriate supply, storage, handling, distribution and usage of

investigational product in accordance with the protocol and any applicable laws and regulations.

Clinical Supplies will be provided by Merck as summarized in Table 7.

Table 7: Product Descriptions

Product Name & Potency	Dosage Form
Pembrolizumab 50 mg	Lyophilized Powder for Injection
Pembrolizumab 100 mg/ 4mL	Solution for Injection
Vorinostat 100 mg	Capsules

11.2 Packaging and Labeling Information

Clinical supplies will be affixed with a clinical label in accordance with regulatory requirements.

11.3 Clinical Supplies Disclosure

This trial is open-label; therefore, the subject, the trial site personnel, the Sponsor and/or designee are not blinded to treatment. Drug identity (name, strength) is included in the label text; random code/disclosure envelopes or lists are not provided.

11.4 Storage and Handling Requirements

Clinical supplies must be stored in a secure, limited-access location under the storage conditions specified on the label.

Receipt and dispensing of trial medication must be recorded by an authorized person at the trial site.

Clinical supplies may not be used for any purpose other than that stated in the protocol.

11.5 Returns and Reconciliation

The investigator is responsible for keeping accurate records of the clinical supplies received from Merck, or designee, the amount dispensed to and returned by the subjects and the amount remaining at the conclusion of the trial.

Upon completion or termination of the study, all unused and/or partially used investigational product will be destroyed at the site per institutional policy. It is the Investigator's responsibility to arrange for disposal of all empty containers, provided that procedures for proper disposal have been established according to applicable federal, state, local and institutional guidelines and procedures, and provided that appropriate records of disposal are kept.

12.0 ADMINISTRATIVE AND REGULATORY DETAILS

12.1 Compliance with Trial Registration and Results Posting Requirements

Under the terms of the Food and Drug Administration Modernization Act (FDAMA) and the Food and Drug Administration Amendments Act (FDAAA), the Sponsor of the trial is solely responsible for determining whether the trial and its results are subject to the requirements for submission to the Clinical Trials Data Bank, <http://www.clinicaltrials.gov>. Information posted will allow subjects to identify potentially appropriate trials for their disease conditions and pursue participation by calling a central contact number for further information on appropriate trial locations and trial site contact information.

14.0 APPENDICES

14.1 ECOG Performance Status

Grade	Description
0	Normal activity. Fully active, able to carry on all pre-disease performance without restriction.
1	Symptoms, but ambulatory. Restricted in physically strenuous activity, but ambulatory and able to carry out work of a light or sedentary nature (e.g., light housework, office work).
2	In bed <50% of the time. Ambulatory and capable of all self-care, but unable to carry out any work activities. Up and about more than 50% of waking hours.
3	In bed >50% of the time. Capable of only limited self-care, confined to bed or chair more than 50% of waking hours.
4	100% bedridden. Completely disabled. Cannot carry on any self-care. Totally confined to bed or chair.
5	Dead.

* As published in Am. J. Clin. Oncol.: *Oken, M.M., Creech, R.H., Tormey, D.C., Horton, J., Davis, T.E., McFadden, E.T., Carbone, P.P.: Toxicity And Response Criteria Of The Eastern Cooperative Oncology Group. Am J Clin Oncol 5:649-655, 1982.* The Eastern Cooperative Oncology Group, Robert Comis M.D., Group Chair.

14.2 Common Terminology Criteria for Adverse Events V4.0 (CTCAE)

Due to the size of the latest version of the Common Toxicity Criteria, copies of this appendix are not included with this protocol document. An electronic copy is available on the CTEP web site, <http://ctep.cancer.gov/reporting/ctc.html>.

14.3 Response Evaluation Criteria in Solid Tumors (RECIST) 1.1 Criteria for Evaluating Response in Solid Tumors

RECIST version 1.1* will be used in this study for assessment of tumor response. While either CT or MRI may be utilized, as per RECIST 1.1, CT is the preferred imaging technique in this study. The same imaging technique regarding modality, ideally the same scanner, and the use of contrast should be used in a participant throughout the study to optimize the reproducibility of the assessment of existing and new tumor burden and improve the accuracy of the assessment of response or progression based on imaging.

* As published in the European Journal of Cancer:

E.A. Eisenhauer, P. Therasse, J. Bogaerts, L.H. Schwartz, D. Sargent, R. Ford, J. Dancey, S. Arbuck, S. Gwyther, M. Mooney, L. Rubinstein, L. Shankar, L. Dodd, R. Kaplan, D. Lacombe, J. Verweij. New response evaluation criteria in solid tumors: Revised RECIST guideline (version 1.1). Eur J Cancer. 2009 Jan;45(2):228-47.

In addition, volumetric analysis will be explored by central review for response assessment.

14.3.1 Tumor Imaging and Assessment of Disease

Tumor imaging is strongly preferred to be acquired by computed tomography (CT). For the abdomen and pelvis, contrast-enhanced magnetic resonance imaging (MRI) may be used when CT with iodinated contrast is contraindicated, or when local practice mandates it. MRI is the strongly preferred modality for imaging the brain. The same imaging technique regarding modality, ideally the same scanner, and the use of contrast should be used in a participant throughout the study to optimize the reproducibility of the assessment of existing and new tumor burden and improve the accuracy of the assessment of response or progression based on imaging.

Expedited confirmation of measurable disease based on RECIST 1.1 at Screening should be used to determine participant eligibility. Confirmation that the participant's imaging shows at least 1 lesion that is appropriate for selection as a target lesion per RECIST 1.1 is highly recommended prior to participation starting treatment.

Participant eligibility will be determined using local assessment (Investigator assessment) based on RECIST 1.1. In addition, images (including via other modalities) that are obtained at an unscheduled time point to determine disease progression, as well as imaging obtained for other reasons, but which demonstrate radiologic progression, should also be used to determine progression.

When the Investigator identifies radiographic progression per RECIST 1.1, efforts should be made to verify radiologic PD. Treatment should continue until PD has been verified.

14.3.2 Initial Tumor Imaging

Initial tumor imaging at Screening must be performed within 28 days prior to the date of the first cycle. The site study team must review screening images to confirm the participant has measurable disease per RECIST 1.1.

The screening images must be submitted to the central imaging vendor for confirmation of measurable disease per RECIST 1.1 for eligibility prior to start of treatment.

Tumor imaging performed as part of routine clinical management is acceptable for use as screening tumor imaging if they are of diagnostic quality and performed within 28 days prior to the date of cycle 1 and can be assessed by the central imaging vendor.

14.3.3 Tumor Imaging During the Study

The first on-study imaging assessment should be performed at 4 weeks (28 days -7 days) from the date of screening. Subsequent tumor imaging should be performed every 9 weeks (63 days \pm 3 days) or more frequently if clinically indicated. After 18 weeks (126 days \pm 3 days), participants who remain on treatment will have imaging performed every 9 weeks (63 days \pm 3 days). Imaging timing should follow calendar days and should not be adjusted for

delays in cycle starts. Imaging should continue to be performed until disease progression is identified by the Investigator.

Objective response should be confirmed by a repeat imaging assessment. Tumor imaging to confirm PR or CR should be performed at least 4 weeks after the first indication of a response is observed. Participants will then return to regular scheduled imaging every 9 weeks, starting with the next scheduled imaging time point. Participants who receive additional imaging for confirmation do not need to undergo the next scheduled tumor imaging if it is less than 4 weeks later; tumor imaging may resume at the subsequent scheduled imaging time point.

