Once the RP2D is identified, the Dose Expansion Phase will be opened. During the Dose Expansion Phase, the study will have a run-in phase with sequential single-agents (Schema B) and then the combination phase (Schema A). The run-in phase may be waived at the investigator's discretion. The reason for the run-in phase during dose expansion is to obtain data on the immunomodulatory effects of vorinostat separately from pembrolizumab. Forty-five patients with prior treatments will be enrolled in three expansion cohorts: 15 anti-PD1 naive renal and urothelial patients, 15 anti-PD1 resistant renal and urothelial patients (defined as patients with transient clinical response or without clinical response to prior immune-checkpoint inhibition), and 15 patients with androgen-sensitive or castration-resistant prostate cancer. The prostate cohort has been added in an amendment during the Dose Expansion Phase, and therefore, will not be part of the Dose Finding Phase.

Anti-tumor activity will be assessed by radiological tumor assessments conducted at baseline, 12 weeks and every 6 weeks thereafter, using RECIST version 1.1 (see Section 14.3). RECIST 1.1 will be used for treatment decisions until first radiologic evidence of progressive disease (PD). Following the first evidence of radiologic PD, treatment decisions may be made by the adaption of RECIST 1.1, termed the immune-related response criteria (irRC) (see Section 14.6) to account for the tumor response patterns seen with pembrolizumab treatment (e.g. tumor flare).

[figure not shown]
1 Cycle = 3 weeks (21 days)

Schema B: Run-In Phase

The RP2D is the dose of pembrolizumab and vorinostat in combination chosen for further clinical development. Further experience in the Dose Expansion Cohort may result in a RP2D dose lower than the MTD.

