Correlative Studies Blood Collection	x	x ⁸	x	x	x	x	x	x	x	x	x ¹⁰				

Footnotes:

¹ Procedures completed prior to consenting that are a part of a subject's standard of care may be used if they fall within the 28 day window to start treatment. Screening procedures completed 7 days of C1D1 do not need to be repeated.

² If the subject discontinues treatment due to disease progression, a phone call to the patient can serve as the Safety Follow-up Visit if the End of Treatment Visit was done. If a subject initiates a new anti-cancer therapy within 30 days after the treatment discontinuation, the 30 day Safety Follow-up Visit must occur before the first dose of the new therapy. Once new anti-cancer therapy has been initiated the subject will move into Survival Follow-up.

³ Applies to subjects who discontinue trial treatment for a reason other than disease progression. Subjects should be assessed per institutional guidelines by radiologic imaging to monitor disease status. Every effort should be made to collect information regarding disease status until the start of new anti-neoplastic therapy, disease progression, death, end of the study or if the subject begins retreatment with pembrolizumab.

⁴ Full physical exams may also be done by the investigator or qualified designee throughout participation in the trial as clinically indicated.

⁵ Only if clinically indicated and must be completed \leq 7 days prior to the first dose of study medication

⁶ It is recommended that after 1 year, imaging should be done every 6 months \pm 2 weeks; however, institutional guidelines and investigator discretion may vary.

⁷ Whenever possible, archival tissue from a tumor lesion will be obtained at screening. However, patients will be given the option to consent to a biopsy during the screening phase in case archival tissue cannot be retrieved and a second biopsy on Cycle 1 Day 14 (- 3 days). Missed tissue collection will not be considered a protocol deviation for the purposes of this study, as tissue collection is an exploratory objective for this study.

⁸ Run-in Phase, Cycle -2 Days 1 and 14

⁹ Laboratory tests for screening or entry into the Retreatment Phase should be performed within 10 days prior to the first dose of treatment. After Cycle 1, pre-dose laboratory procedures can be conducted up to 72 hours prior to dosing. Results must be reviewed by the investigator or qualified designee and found to be acceptable prior to each dose of trial treatment.

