¹⁰ When patients are taken off treatment and at the time of disease progression blood for correlative markers will be also obtained.

¹¹ HgbA1c only required for patients with diabetes mellitus at time of study entry.

¹² Only as clinically indicated (Cohort A and B). Standard of care after initial ⁶⁸Ga-PSMA-11 PET (Cohort C)

¹³ Imaging will be done prior to dosing on C3D1.

¹⁴ The run-in phase will only be done during the Dose Expansion Phase and may be waived at the investigator's discretion.

¹⁵ Window for second biopsy is -3 days not +/- 3 days as is the case for other procedures at this time point. Biopsy should occur approximately 2 hours following the most recent dose of vorinostat on cycle 1 day 14. To ensure that these samples are obtained at the correct time, patients are urged to take their vorinostat dose in the clinic on the day of on-treatment sample collection.

¹⁶ Imaging will be done every 3 cycles beginning cycle 6 throughout treatment.

¹⁷ Applicable to a subset of patients in Cohort C (prostate cancer) only, as determined by the Principal Investigator. The Ga-PSMA-11 PET scan should be completed at 12 weeks (C4D1)

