7.1.2.5 Tumor Imaging and Assessment of Disease

Imaging studies (CT and bone scan) will be performed at baseline, before Cycle 3, every 3 cycles thereafter and at treatment discontinuation as described in Section 7.1.4.1 below. CT modalities should be done according to standard of care for the patient's disease. Bone scans should be done at baseline and then only as clinically indicated.

Patients in Cohort C (prostate) will have two PET scans using ⁶⁸Ga-PSMA-11: once at baseline and then at 12 weeks (Cycle 4) Not all patients in Cohort C will have the additional PET scans. This determination will be made by the Principal Investigator.

Participant eligibility will be determined using local assessment (Investigator assessment) based on RECIST 1.1. In addition, images (including via other modalities) that are obtained at an unscheduled time point to determine disease progression, as well as imaging obtained for other reasons, but which demonstrate radiologic progression, should also be used to determine progression.

When the Investigator identifies radiographic progression per RECIST 1.1, efforts should be made to verify radiologic PD. Treatment should continue until PD has been verified. Regardless of whether PD is verified, if the Investigator considers the participant has progressed, but elects to implement irRC, the Investigator will assess for confirmation of progression by irRC at subsequent time points.

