14.3.4 End of Treatment and Follow-up Tumor Imaging

In participants who discontinue study treatment, tumor imaging should be performed at the time of treatment discontinuation (± 4 week window). If previous imaging was obtained within 4 weeks prior to the date of discontinuation, then imaging at treatment discontinuation is not mandatory. In participants who discontinue study treatment due to documented disease progression and the investigator elects not to implement iRECIST, this is the final required tumor imaging.

For participants who discontinue study treatment without documented disease progression, every effort should be made to continue monitoring their disease status by tumor imaging using the same imaging schedule used while on treatment (every 9 weeks in Year 1 or every 6 months after Year 1) to monitor disease status until the start of a new anticancer treatment, disease progression, pregnancy, death, withdrawal of consent, or the end of the study, whichever occurs first.

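### Three incompatible on-treatment CT calendars serve the ORR/PFS primary objective, and the screening-anchored first scan in Section 14.3.3 can fall on or before first dose

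*Combined protocol and SAP*

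**What the plan says.** Section 3.1 makes objective response rate and PFS the primary objective. The scans behind both are scheduled in several places:

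- **Section 2.1:** "radiological tumor assessments conducted at baseline, 12 weeks and every 6 weeks thereafter, using RECIST version 1.1 (see Section 14.3". The starting point of the 12 weeks is not given.
- **Section 6, footnotes 13 and 16:** "Imaging will be done prior to dosing on C3D1", and "Imaging will be done every 3 cycles beginning cycle 6 throughout treatment". Section 7.1.2.5 agrees: "Imaging studies (CT and bone scan) will be performed at baseline, before Cycle 3, every 3 cycles thereafter and at treatment discontinuation". Section 7.1.2.6.1 repeats it.
- **Section 14.3.3:** "The first on-study imaging assessment should be performed at 4 weeks (28 days -7 days) from the date of screening", then every 63 ± 3 days, with a mark at 18 weeks (126 days). It adds: "Imaging timing should follow calendar days and should not be adjusted for" delays in cycle starts.

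Section 14.3.2 allows screening imaging up to 28 days before the first cycle. Sections 7.1 and 7.1.5 point to Section 6 for visit procedures, but no passage says that Section 6 overrides Section 14.3.3.

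Two further passages bear on imaging after Year 1. Section 14.3.4 refers to "the same imaging schedule used while on treatment (every 9 weeks in Year 1 or every 6 months after Year 1", and Section 6 footnote 6 says: "It is recommended that after 1 year, imaging should be done every 6 months", subject to institutional guidelines and investigator discretion.

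Section 8.9 estimates PFS by Kaplan-Meier and names no time origin.

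**The concern.** Progression found at a scheduled scan is dated by the scan calendar and measured from a time origin. Here the calendar is contradictory on four counts (first scan, anchor, interval, and whether scans move with cycle delays), and the origin is unstated. Sites following different sections would date the same disease course differently within one 15-patient cohort.

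The 14.3.3 anchor is also a fault in itself. A first on-study scan counted from screening can be due before any drug has been given, so it would be a second baseline rather than an assessment of treatment. Section 8.4 calls the expansion cohorts critical for planning the next phase, so the way their PFS is measured should be reproducible.

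**Working it through.** **Inputs.** Cycle length 21 days (Section 2.1). Screening imaging d days before first dose, 0 ≤ d ≤ 28 (14.3.2). First 14.3.3 scan 21 to 28 days after screening. Cohort size 15 (8.4). Assumptions: the screening date in 14.3.3 is the screening imaging date, and the first cycle starts with the first dose. If a run-in is given, it is two 21-day cycles; Section 6 lists Cycles -2 and -1, but the Schema B figure is not shown.

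**1. The plan's own figures.** 4 × 7 = 28 days, 9 × 7 = 63 days, 18 × 7 = 126 days. Three cycles are 3 × 21 = 63 days. Section 6 and 14.3.3 therefore agree on a 9-week interval. Section 2.1, at 6 × 7 = 42 days, is the outlier.

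**2. First scan, Section 2.1 against Section 6.** Day 1 of Cycle k is (k − 1) × 21 days after C1D1, plus 42 days from first dose after a full run-in.
- No run-in: C3D1 = 2 × 21 = day 42, week 6. This conflicts with week 12.
- Full run-in: 42 + 42 = day 84, week 12. This matches Section 2.1.

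The match holds only for expansion patients who receive the full run-in. It fails when the run-in is waived and in the Dose Finding Phase.

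**3. First and second scan, Section 14.3.3.** Relative to first dose, the first window is day 21 − d to 28 − d. The second, 63 days later, is day 84 − d to 91 − d.

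| d | First scan (day) | Second scan (day) |
|---|---|---|
| 28 | −7 to 0 | 56 to 63 |
| 21 | 0 to 7 | 63 to 70 |
| 20 | 1 to 8 | 64 to 71 |
| 0 | 21 to 28 | 84 to 91 |

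The first window touches or precedes first dose for d = 21 to 28, and lies wholly on or before it only at d = 28. The second scan falls at about weeks 8 to 13.

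**4. Cycle delay.** A 2-week delay before Cycle 3 moves the Section 6 scan from week 6 to week 8. The 14.3.3 scan does not move.

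**5. Effect on the observed median.** The documents give no PFS assumption, so I take exponential PFS with true median m = 13.0 or 17.4 weeks, full follow-up, and every progression dated at the next scheduled scan. The median of 15 is the 8th ordered time, and G(t) = P(8th time ≤ t) = P(Binomial(15, 1 − 2^(−t/m)) ≥ 8). The mean observed median is the sum over scan times s_k of s_k × [G(s_k) − G(s_(k−1))].

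| Calendar (weeks from first dose) | m = 13.0: mean (SD) | m = 17.4: mean (SD) |
|---|---|---|
| 2.1: 12, 18, 24, ... | 16.79 (4.9) | 21.25 (6.7) |
| Section 6, no run-in: 6, 15, 24, ... | 18.14 (5.4) | 22.70 (7.1) |
| Section 6, full run-in: 12, 21, 30, ... | 18.02 (5.7) | 22.70 (7.1) |
| 14.3.3, d = 0 to 28 | 18.02 to 18.19 (5.5 to 5.7) | 22.69 to 22.73 (7.0 to 7.1) |

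Section 2.1 against Section 6 without run-in: 18.14 − 16.79 = 1.35 weeks and 22.70 − 21.25 = 1.45 weeks. Section 6 against 14.3.3: about 0.1 week or less. If 30% of events are dated at their true time (an assumption), simulation gives gaps of 16.97 − 16.11 = 0.86 and 21.50 − 20.47 = 1.03 weeks.

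The 14.3.3 row chains 63 days from the first scan. That puts the third scan at day 147 − d to 154 − d, which in general misses the 126-day mark. A reading that fits the mark, with scans at weeks 9, 18, 27 from first dose, gives 18.15 and 22.73, so the conclusion does not depend on this choice.

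**The case against.** The strongest reply is that a workable calendar exists. Section 6, 7.1.2.5 and 7.1.2.6.1 agree with each other, and 7.1 and 7.1.5 send sites to Section 6. Section 8.9 excludes Dose Finding patients when efficacy is estimated for a future trial. Expansion patients receive the run-in unless it is waived, and with a two-cycle run-in Section 2.1's week 12 is C3D1. Analyses are descriptive with no comparisons, and unscheduled scans showing progression also count (7.1.2.5, 14.3.1).

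Much of this stands. It narrows the first-scan conflict between Sections 2.1 and 6 and keeps the numerical effect small. It does not remove the 6- versus 9-week interval, the waived run-in, or 14.3.3, whose anchor and calendar rule contradict Section 6 in every phase. Nor does any passage set precedence: Section 2.1 itself sends the reader to 14.3 for RECIST.

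A reader might infer that a scan taken before treatment leaves patients non-evaluable. The documents do not support that. Section 8.4 accepts any later scan, or symptomatic deterioration, after one combination cycle, and 8.3.1 sets no cycle condition. A reader might also infer a material bias in the primary results. The figures above do not show one, and no change in response rate can be computed.

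The post-Year-1 conflict is weaker evidence. Footnote 6 is only a recommendation and its marker is not visible in the extracted table, while the 14.3.4 wording sits in a paragraph about patients who have stopped treatment.

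**Conclusion.** The point holds and is minor. Three on-treatment CT calendars coexist and cannot all be followed. Section 2.1 is the outlier on interval, and its first scan agrees with Section 6 only after a full two-cycle run-in. As written, 14.3.3 allows the first on-study scan on or before first dose for screening imaging 21 to 28 days before, and requires it at 28 days.

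The only visible effect on estimates is about 1.4 weeks in a cohort's observed median PFS, from Section 2.1's 6-week interval, against a cohort SD of 5 to 7 weeks. That size rests on the assumed exponential PFS, the assumed medians and scan-dated progression; off-schedule dating shrinks it. The calendar contradictions themselves need no such assumption. The pre-dose result needs only that screening means the screening imaging date.

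**What to change.** In one amendment:

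- Reconcile Sections 2.1, 6, 7.1.2.5, 7.1.2.6.1 and 14.3.3 to a single imaging calendar, chosen by the sponsor from the intervals already in the protocol, and state which section governs.
- Replace the screening anchor in 14.3.3 with a stated treatment date, so that the first on-study scan cannot precede treatment. Section 14.3.5 already does this by counting from the restart of treatment.
- Say whether scans move with cycle delays.
- Name the same anchor in Section 8.9 as the PFS time origin, for patients with and without the run-in. Otherwise origins within a cohort could differ by 42 days (6 weeks).
- Tidy up two side issues. Reconcile the frequency after Year 1 (14.3.4 and footnote 6 against footnote 16 and 14.3.3). Correct the PSMA-PET label in footnote 17 and 7.1.2.5, which equates 12 weeks with Cycle 4: C4D1 is 3 × 21 = 63 days, week 9 from C1D1, or week 15 from first dose after a full run-in.
- For patients already scanned, keep the actual scan dates and report which calendar was followed.

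The cost is wording. Keeping the 9-week interval adds no scheduled scans relative to Section 6. The 6-week interval would mean 16 scans by week 104 (weeks 12, 18, ..., 102) instead of 11 (weeks 6, 15, ..., 96) for a patient still on treatment. Scans already done cannot be re-timed.
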